5.16. Exploratory Analysis

The population for all exploratory analyses is the ITT population, which treats all postrescue therapy measurements as missing (efficacy estimand) with all scheduled postdose visit data up to Week 52 (Visit 16) unless otherwise stated.

5.16.1. *Parameters of Interest*

The exploratory parameters of interest include, but are not limited to, the following measurements in change from baseline to Week 26 and 52 (unless otherwise specified):

- HbA1c to Week 13 (Visit 6)
- Percentage of patients reaching HbA1c target of:
 - $\leq 6.5\%$
 - $\leq 6.5\%$ without severe, documented symptomatic (blood glucose [BG] <70 mg/dL), or probable hypoglycemic episodes
 - $<7.0\%$ without severe, documented symptomatic (BG <70 mg/dL), or probable hypoglycemic episodes
- Body weight
- BMI standard deviation score (SDS)
- Height and height SDS
- Waist circumference
- Measures of insulin resistance, beta cell function, and serum adiponectin at Weeks 13 and 26

- Change in basal insulin dose from baseline to Week 26 and from baseline to Week 52

5.16.2. *Analysis on HbA1c Change from Baseline to Week 13*

The same MMRM model as that described in Section 5.11.1 will be used. The Week 13 data will be included in the analysis of the data through Week 26 and through Week 52.

5.16.3. *Analysis of Percentage of Patients Reaching HbA1c Target*

The same model as that described in Section 5.12.1 for the percentage of patients reaching a HbA1c target of <7% will be applied for 3 parameters of interests: HbA1c \leq 6.5%, composite endpoint of HbA1c <7% without severe, documented symptomatic (BG <70 mg/dL), or probable hypoglycemic episodes, and HbA1c \leq 6.5% without severe, documented symptomatic (BG <70 mg/dL), or probable hypoglycemic episodes. Detailed hypoglycemia episodes are defined in Section 5.15.2.1.

Additional analysis will be performed on the ITT population using logistic regression defined in Section 5.12.2 for Week 26 and Week 52, where patients who have been rescued or have missing data at Week 26 or Week 52 will be imputed to have not achieved the target, while for nonrescued patients the available data will be used.

5.16.4. *Analysis of Change in Body Weight, BMI SDS, Height and Waist Circumference*

The standard MMRM approach detailed in Section 5.2 for analyzing continuous data will be used to analyze change from baseline in body weight, BMI SDS, height, height SDS, and waist circumference. When analyzing height, sex will also be included in the model as a covariate since this is a prognostic factor for height in children and adolescents. For BMI and height, SDS will be calculated for each subject based on age and sex using World Health Organization standards and methods (WHO 2008) and analyzed as described above.

5.16.5. *Analysis of Change in Basal Insulin Dose*

Descriptive summary statistics will be presented for the change from baseline in basal insulin dose in both U/Day and U/kg/Day for each treatment at each visit from baseline to Week 26 and from baseline to Week 52.

5.16.6. *Pharmacodynamic Endpoints on Insulin Sensitivity and β -Cell Function*

The endpoints include HOMA2-%B, HOMA2-IR, 1/fasting insulin or 1/fasting C-peptide, and adiponectin. HOMA1-%B is used in Lilly original proposal to FDA. However, HOMA1 as the original model developed in 1985 did not account for differences between hepatic and peripheral insulin sensitivity, increases in insulin secretion, or decreases in hepatic glucose production for plasma glucose concentrations above 180 mg/dL, renal glucose losses, or the contribution of circulating proinsulin. In addition, the original HOMA model (HOMA1) uses equations that were calibrated to insulin assays used in the 1970s, which result in underestimation of %-S and

overestimation of %-B. An updated HOMA model (HOMA2) has been created to account for these variations. With knowledge of these differences, it is therefore important for this study to use HOMA2 instead of HOMA1 to quantify insulin resistance and beta-cell function.

The estimated insulin sensitivity scores will be calculated as follows: $\log_e IS = 4.64725 - 0.02032$ (waist, cm) – 0.09779 (HbA1c, %) – 0.00235 (TG; mg/dl).

The normality assumption of each biomarker will be assessed both visually (histogram and QQ-plot) and through the Shapiro-Wilk test prior to the formal statistical analysis.

The MMRM model will be fitted for each biomarker separately with stratification factors, treatment, time, visit-by-time interaction as fixed effect, subject as a random effect, and corresponding baseline as a covariate. If data are normal distributed, change from baseline will be the parameter of interest. If data are log normal distributed, log (ratio relative to baseline) will be the parameter of interest.

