7.1. Summary of Study Design

Study H9X-MC-GBGC (GBGC) is a Phase 3, multicenter, randomized, double-blind, parallel-arm, placebo-controlled superiority trial with an open-label extension. Approximately 150 male and female children and adolescents (ages 10 to <18 years) with T2DM and inadequate glycemic control on diet and exercise alone or diet and exercise plus metformin and/or basal insulin will be enrolled. Randomization will be stratified by the patient's background therapy, and screening HbA1c. There will be a limitation on the number of patients with inadequate glycemic control managed by diet and exercise alone who have not previously received metformin so that these patients constitute no more than 25% of the total number of completers. The sponsor may place limitations on the patients enrolled depending on their demographics to meet regulatory expectations.

The main study has 4 periods: (1) a screening period lasting up to 4 weeks; (2) a double-blind treatment period lasting 26 weeks; (3) an open-label extension period lasting 26 weeks; and (4) a 30-day safety follow-up period. The end of trial is the date of the last visit or last scheduled procedure shown in the Study Schedule ([Attachment 1](#)) for the last patient.

One of the following measures will be offered to reduce pain associated with venipuncture: anesthetic creams, anesthetic patches, or high pressure anesthetic delivery system immediately before venipuncture.

Patients are discouraged from donating blood or blood products during the trial and for 30 days thereafter.

Figure [GBGC.1](#) illustrates the study design.

[figure not shown]

Figure GBGC.1. Illustration of study design for Clinical Protocol H9X-MC-GBGC.

Screening period: Patients may be rescreened twice for any reason. At the screening visit, during which patients may be in the non-fasted state, the parent or legal guardian will sign the informed consent form (ICF) and the patient will sign the assent form. If the patient has reached the age of majority per local country regulations, a separate assent document may not be required, as the patient is eligible to sign the ICF. The patients will then undergo assessments related to the inclusion and exclusion criteria.

Week -4: Screening Visit

At this visit, the following will be performed:

- A complete medical history will be taken along with full date of birth.
- Vital signs will be measured, along with height and weight, and BMI will be calculated.

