8.1. Inclusion Criteria

Patients are eligible to be included in the study only if they meet all of the following criteria:

- [1] Are male or female children and adolescents aged 10 to <18 years at randomization.
- [2] Have T2DM as diagnosed by Global International Diabetes Foundation/International Society for Pediatric and Adolescent Diabetes (IDF-ISPAD; IDF 2011 [WWW]) criteria (see [Attachment 5](#)).
- [3] Have T2DM treated at the time of randomization with lifestyle measures (standardized diet and exercise program), with or without metformin (≥ 1000 mg/day, unless the patient has documented intolerance of metformin, in which case the highest tolerated dose will be used, and not more than the locally approved dose), and/or basal insulin therapy. Doses of metformin and basal insulin must have been stable ($\pm 15\%$) for at least 8 weeks prior to screening visit. Lifestyle measures must have been in place for at least 8 weeks prior to the screening visit.
- [4] Have HbA1c $>6.5\%$ to $\leq 11.0\%$ at screening visit, unless a patient is newly diagnosed and only treated with lifestyle measures, in which case the HbA1c should be $>6.5\%$ to $\leq 9.0\%$.
- [5] Have BMI $>85\%$ percentile of the general age- and gender-matched population for that country or region and body weight ≥ 50 kg.
- [6] Both the child or adolescent with T2DM and a parent or legal guardian are able to understand and fully participate in the activities of the clinical trial and sign their assent and consent, respectively.

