10.4.2.3. Assessment of Pubertal Progression

Patients’ pubertal progression will be assessed throughout the trial. Tanner staging will be performed at baseline, 26 weeks and 52 weeks: those patients who have reached Tanner stage 5 will not be evaluated again. Morning hormone levels (estradiol, testosterone in males, LH, IGF-1, cortisol, and prolactin) will be performed at baseline, 26 weeks, and 52 weeks.

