4.3. Exploratory Objectives

The exploratory objectives are to compare the dulaglutide 0.75 mg and dulaglutide 1.5 mg arms (individually and pooled) to placebo with respect to the following parameters at 26 weeks, and to assess the following parameters in the dulaglutide 0.75 mg and dulaglutide 1.5 mg arms (individually and pooled) at Week 52 (unless otherwise specified):

- Percentage of patients with HbA1c $\leq 6.5\%$ at Weeks 26 and 52
- Change in HbA1c between baseline and Week 13
- Percentage of patients having HbA1c $\leq 6.5\%$ without severe, documented symptomatic (<70 mg/dL), or probable hypoglycemic episodes at Weeks 26 and 52
- Percentage of patients having HbA1c $< 7.0\%$ without severe, documented symptomatic (<70 mg/dL), or probable hypoglycemic episodes at Weeks 26 and 52
- Change in weight between baseline and Weeks 26 and 52
- Change in hormone-related safety assessed by the effect on morning serum prolactin, insulin-like growth factor-1 (IGF-1), estradiol, testosterone (males only), luteinizing hormone (LH), and cortisol between baseline and Weeks 26 and 52
- Change in serum lipids between baseline and Weeks 26 and 52
- Change in Tanner staging between baseline and Weeks 26 and 52
- Change in BMI standard deviation score (SDS) between baseline and Weeks 26 and 52
- Change in height and height SDS between baseline and Weeks 26 and 52
- Change in waist circumference between baseline and Weeks 26 and 52
- Change in the EQ-5D-Youth version (EQ-5D-Y) visual analogue scale (VAS) score between baseline and Weeks 26 and 52
- Percentage of patients reporting each level of problem on each dimension of the EQ-5D-Y at baseline and Weeks 26 and 52
- Assess effect of dulaglutide on measures of insulin resistance, beta cell function, and serum adiponectin at Weeks 13 and 26

- Change in basal insulin dose from baseline to Week 26 and from baseline to Week 52

5. A Priori Statistical Methods

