Unless otherwise specified, data listings will consist of all randomized patients. Both efficacy and safety analyses will be conducted using the ITT population. For safety except hypoglycemia analyses, all measurements including those made after taking rescue therapy will be included. Hypoglycemia analyses will be evaluated in the ITT population after censoring the data following administration of any rescue medication.

Unless otherwise specified, all tests of treatment effects will be conducted at a 2-sided alpha level of 0.05 and confidence intervals (CI) will be calculated at 95%, 2 sided.

For subgroup analyses, all tests of interactions between treatment and factors of interest will be conducted at a 2-sided alpha level of 0.10.

Visit 2 is the baseline visit. Baseline measurement for a corresponding parameter of interest is defined as the last nonmissing value taken prior to the first dosing of study drug. Baseline HbA1c value will be used to define HbA1c strata for analyses.

Unless otherwise specified, longitudinal continuous measures will be analyzed using MMRM with stratification factors (insulin usage [yes, no], metformin usage [yes, no], HbA1c strata [HbA1c: <8.0%, $\geq 8.0\%$]), treatment (Dula 1.5, Dula 0.75, Placebo or Placebo/Dula 0.75), visit, and treatment-by-visit as fixed effects, and corresponding baseline measurement as a covariate unless otherwise noted. The Kenward-Roger method will be used to estimate denominator degrees of freedom, and the REML approach to obtain model estimate. An unstructured covariance structure will be used to model the within-patient errors. If this model fails to converge, the following covariance structures will be tested in order:

- Toeplitz with heterogeneity
- Autoregressive with heterogeneity, by visit
- Compound symmetry with heterogeneous variances, by visit
- Toeplitz
- Autoregressive
- Compound symmetry without heterogeneous variances, by visit

The first variance-covariance structure that converges will be used.

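### The exploratory height-change (cm) model adds sex but leaves out baseline age, and so gives up precision in the only randomised growth comparison

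*SAP*

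**What the plan says.** Eligible patients "Are male or female children and adolescents aged 10 to <18 years at randomization" (Protocol 8.1). Change in height and change in height SDS are listed together as one exploratory objective: "Change in height and height SDS between baseline and Weeks 26 and 52" (SAP 4.3).

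The general model in SAP 5.2 contains "stratification factors (insulin usage [yes, no], metformin usage [yes, no], HbA1c strata" and treatment, with "visit, and treatment-by-visit as fixed effects, and corresponding baseline measurement as a covariate unless otherwise noted". For height, SAP 5.16.4 adds one term: "sex will also be included in the model as a covariate since this is a prognostic factor for height in children and adolescents". The centimetre model therefore has insulin use, metformin use, HbA1c stratum, treatment, visit, treatment-by-visit, baseline height and sex. Age and Tanner stage are not in it, and neither is a randomisation stratum (Protocol 9.3).

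Both are available. At screening, "A complete medical history will be taken along with full date of birth" (Protocol 7.1), and "Tanner staging will be performed at baseline, 26 weeks and 52 weeks" (Protocol 10.4.2.3).

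The same SAP paragraph adds a second scale: "For BMI and height, SDS will be calculated for each subject based on age and sex using World Health Organization standards and methods", analysed with the same type of model. SAP 5.2 rules out inference between arms after Week 26, when placebo patients move to dulaglutide.

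**The concern.** By adding sex, the SAP accepts that the standard model is not enough for a growth outcome. But the outcome is change in height, with baseline height already a covariate. What then separates patients is how much growth they have left, and across an age range of 10 to under 18 that should depend on age at least as much as on sex. Two patients of the same sex and height, one aged 11 and one aged 16, have different expected growth over 26 weeks, and the model treats them alike.

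Two things follow, and they are two faces of one problem. The interval for the treatment difference is wider than it need be. And if one arm happens to be younger, the model corrects this only as far as baseline height and sex stand in for age. Week 26 is the only randomised comparison of growth, with about 40 placebo completers, so later data cannot recover the lost precision.

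**Working it through.** **Plan's own figure.** There is none: neither document gives an SD, an effect size or a precision target for height. What follows is a sensitivity calculation under stated assumptions.

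**Sample.** SAP 5.1 plans 150 patients (50 per arm) with 20% dropout, so 150 × 0.8 = 120 completers: 80 pooled dulaglutide and 40 placebo. The standard error (SE) of the Week 26 difference is residual SD × √(1/80 + 1/40) = residual SD × 0.1936.

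**Closed form.** Let R² be the share of the variance left after baseline height and sex that age explains. Then planned SE ÷ age-adjusted SE = 1/√(1 − R²).

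| R² | SE ratio | Cut in SE, 1 − √(1 − R²) |
|---|---|---|
| 0.10 | 1.05 | 5% |
| 0.20 | 1.12 | 11% |
| 0.30 | 1.20 | 16% |
| 0.50 | 1.41 | 29% |

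**Simulation, assumed S-shaped growth curves** (200,000 patients per scenario, 65% girls). Growth velocity is vmax/(1 + exp((age − c)/w)) cm per year, with individual variation in c. Only the Week 26 change is modelled, without the background-therapy and HbA1c strata.

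| Scenario | vmax | c boys/girls (w), timing SD | Error SD of change | Ages | Residual SD: height + sex → + age | SE, cm | Cut |
|---|---|---|---|---|---|---|---|
| Weak age signal | 4 | 14.5/12.5 (0.8), 1.0 y | 0.8 cm | 10–18, older-weighted | 0.941 → 0.864 | 0.182 → 0.167 | 8% |
| Middle | 6 | 14.5/12.5 (0.8), 1.0 y | 0.6 cm | 10–18, centred | 0.982 → 0.788 | 0.190 → 0.153 | 20% |
| Strong | 7 | 15/13 (0.6), 0.7 y | 0.4 cm | 10–18, uniform | 1.077 → 0.701 | 0.209 → 0.136 | 35% |
| Older patients | 6 | 14.5/12.5 (0.8), 1.0 y | 0.6 cm | 12–18, older-weighted | 0.796 → 0.731 | 0.154 → 0.141 | 8% |

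In the middle scenario the 95% half-width falls from 1.96 × 0.190 = 0.37 cm to 1.96 × 0.153 = 0.30 cm.

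**Other assumed curves.** With 26-week growth of 2 to 4 cm at age 10 falling in a straight line to zero at 15 (girls) or 17 (boys), and measurement SD 0.3 to 0.7 cm, 18 combinations gave cuts of 4% to 32%. A further set gave 9% to 38%, and 9% to 30% with ages starting at 12. If growth is made an exact function of age and sex and measurement error is small, cuts reach 57%. I leave that out of the range because it ignores differences in pubertal timing among patients of the same age. With a one-year SD in timing, the straight-line curves stay within 4% to 38%.

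**Other terms.** Adding age-by-sex after age moves the residual SD from 0.864 to 0.858, 0.788 to 0.786, 0.701 to 0.701 and 0.731 to 0.709, a reduction of 3% at most. Adding pubertal stage as well gives 0.811, 0.644, 0.464 and 0.637, but the simulated stage follows pubertal timing without staging error, so these are best cases. No gain from stage in the height SDS model was computed.

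**Chance imbalance.** With ages uniform over 10 to 18, the SD of age is 8/√12 = 2.31 years. For 100 against 50 randomised, the SE of the difference in mean age is 2.31 × √(1/100 + 1/50) = 0.40 years. A gap above 0.5 year (z = 0.5/0.40 = 1.25) then arises in about 21% of trials.

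**The case against.** The strongest reply is that age is already dealt with: height SDS is standardised for age and sex and analysed beside centimetre height. This stands, and it rules out the reading that the plan never looks at growth with age accounted for. It does not settle the matter, because centimetre height is a stated endpoint with its own model, the SAP does not say which scale leads, and SDS does not allow for pubertal stage. The source for the SDS is also unclear: SAP 5.16.4 cites a 2008 WHO reference, while the SAP reference list has only a 2006 WHO growth-standards entry.

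A reader might also infer that normal growth as a whole sits in the error term. It does not. The visit terms absorb average growth, and baseline height and sex absorb part of the spread. Only the age-related variation left over is at issue.

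Nor do the documents support a charge of bias. Randomisation keeps the false-positive rate at its nominal level over repeated trials, and an imbalance would be visible, since SAP 5.6 summarises demographics and baseline Tanner stage by arm.

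The 50 kg minimum weight (Protocol 8.1) probably thins out the youngest patients. Protocol 9.4 puts a 10-year-old with a BMI of 23 kg/m² at about 40 kg. That points away from the uniform-age scenarios, but a gain remains when ages start at 12.

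Finally, the endpoint is exploratory and outside the testing hierarchy, and no document states a height difference that would matter. No conclusion of the trial is shown to change.

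**Conclusion.** The point holds as a modest loss of efficiency in an exploratory analysis. The centimetre height model omits a baseline value that is collected and should predict the outcome after baseline height and sex. The direction is firm. The size, a cut in the Week 26 standard error of roughly 4% to 38%, depends on assumed growth curves, measurement error and age mix, none of which the documents supply. The loss is one of precision, with some chance imbalance left uncorrected, and it does not touch the primary or key secondary results.

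It would go too far to say that the model must also include Tanner stage. Stage is the one growth factor missing from both the centimetre and the SDS analyses, but its gain is not established.

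**What to change.** In SAP 5.16.4, add baseline age (continuous, from date of birth) and age-by-visit to the height (cm) model, keeping baseline height and sex. Age-by-visit is needed because growth accumulates: age should matter little for change at Week 4 and more at Week 26. Age-by-sex can be left out.

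Baseline Tanner stage in the height and height SDS models is optional. If it is used, the categories should be grouped in advance so that sparse early stages do not cause trouble.

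The cost is SAP wording and no new data. Age and age-by-visit use one degree of freedom per post-baseline visit: three through Week 26 (Weeks 4, 13 and 26) and five through Week 52 (adding Weeks 39 and 52). The change should be made before unblinding at the primary database lock. After that, the age-adjusted model should be reported as a supplementary analysis and labelled as such.

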6.3. Exploratory Objectives

The exploratory objectives are to compare the dulaglutide 0.75 mg and dulaglutide 1.5 mg arms (individually and pooled) to placebo with respect to the following parameters at 26 weeks, and to assess the following parameters in the dulaglutide 0.75 mg and dulaglutide 1.5 mg arms (individually and pooled) at Week 52 (unless otherwise specified):

- Percentage of patients with HbA1c $\leq 6.5\%$ at Weeks 26 and 52
- Change in HbA1c between baseline and Week 13
- Percentage of patients having HbA1c $< 7.0\%$ without severe, documented symptomatic (< 70 mg/dL), or probable hypoglycemic episodes at Weeks 26 and 52
- Percentage of patients having HbA1c $\leq 6.5\%$ without severe, documented symptomatic (< 70 mg/dL), or probable hypoglycemic episodes at Weeks 26 and 52
- Change in weight between baseline and Weeks 26 and 52
- Change in hormone-related safety assessed by the effect on morning serum prolactin, insulin-like growth factor-1 (IGF-1), estradiol, testosterone (males only), luteinizing hormone (LH), and cortisol between baseline and Weeks 26 and 52
- Change in serum lipids between baseline and Weeks 26 and 52
- Change in Tanner staging between baseline and Weeks 26 and 52
- Change in BMI standard deviation score (SDS) between baseline and Weeks 26 and 52
- Change in height and height SDS between baseline and Weeks 26 and 52
- Change in waist circumference between baseline and Weeks 26 and 52
- Change in the EQ-5D-Y VAS score between baseline and Weeks 26 and 52
- Percentage of patients reporting each level of problem on each dimension of the EQ-5D-Y at baseline, weeks 26 and 52
- Assess the effect of dulaglutide on measures of insulin resistance, beta cell function, and serum adiponectin at Weeks 13 and 26
- Change in basal insulin dose from baseline to Week 26 and from baseline to Week 52

7. Investigational Plan

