10.1.3. Exploratory Efficacy Measures

- Percentage of patients with HbA1c ≤6.5% at Weeks 26 and 52
- Change in HbA1c between baseline and Week 13
- Percentage of patients having HbA1c ≤6.5% without severe, documented symptomatic (<70 mg/dL), or probable hypoglycemic episodes at Weeks 26 and 52
- Percentage of patients having HbA1c <7.0% without severe, documented symptomatic (<70 mg/dL), or probable hypoglycemic episodes at Weeks 26 and 52
- Change in weight from baseline to Week 26 and Week 52
- Change in waist circumference from baseline to Week 26 and Week 52
- Measures of insulin resistance and beta cell function (HOMA-IR, HOMA-%B, 1/fasting insulin) and estimated insulin sensitivity score at Weeks 0, 13, and 26

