For continuous variables, summary statistics will include the number of patients, mean, SD, median, minimum, and maximum for both the actual and change from baseline for each treatment group at each visit. If a patient has no postbaseline data, the patient will be excluded from inferential statistical analysis. For data collected prior to first dosing, or randomization date if the first dosing date is not available, an analysis of variance (ANOVA) model with treatment (Dula 0.75, Dula 1.5, and Placebo) will be fitted. For post-first dosing longitudinal data, the aforementioned MMRM model will be fitted. For nonlongitudinal endpoint data, an ANCOVA model will be fitted by removing visit and visit-by-treatment interaction terms from its corresponding aforementioned MMRM model. Least-squares mean (LSmean) and standard errors derived from the corresponding statistical model will also be displayed for the change from baseline at each visit for each treatment group. Treatment comparisons at the same visit will be displayed showing the LSmean and the 95% CIs for the treatment differences (All Dula – Placebo; Dula 1.5 – Placebo; Dula 0.75 – Placebo) at the same visit along with the corresponding p-values up to Week 26. Appropriate estimate statements will be constructed in each aforesaid model (ANOVA, MMRM, or ANCOVA) to obtain a corresponding endpoint estimate for All Dula and the treatment comparison between All Dula and placebo at each visit of interest up to Week 26.

Unless otherwise stated, categorical variables will be summarized by sample size, frequency, and percentages for each treatment group at each visit. Fisher's exact test will be used to compare the difference among the 3 treatment groups and between All Dula and placebo.

For LOCF, the last nonmissing value will be imputed as the endpoint if the endpoint is missing. Any missing component of date and/or time may be imputed following Lilly standards.

Additional analyses may be performed even after datalock if deemed needed.

All statistical analyses will be conducted with R or SAS Version 9.4® or higher unless otherwise stated.

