5.18. Patient-Reported Outcome Analyses

All PRO analyses are exploratory. Demographic and baseline characteristics of the pediatric population at baseline for HO population will be summarized. The EQ-5D-Y is a standardized generic measure of health status developed by the EuroQol Group. The EQ-5D-Y consists of the EQ-5D-Y descriptive system and the EQ VAS. The descriptive system comprises the same 5 dimensions as the EQ-5D 3 level (EQ-5D-3L), but using a child-friendly wording (mobility; looking after myself; doing usual activities; having pain or discomfort; and feeling worried, sad, or unhappy). Each dimension has 3 levels: no problems, some problems, or a lot of problems. The EQ VAS records the respondent's self-rated health on a vertical VAS where the endpoints are labelled "The best health you can imagine" and "The worst health you can imagine." This VAS information can be used as a quantitative measure of the perception of their overall health by the individual respondents.

The EQ-5D-Y health states, defined by the EQ-5D descriptive system, will be converted into a single index value by applying a formula that essentially attaches value (also called weights) to each of the levels in each dimension. However, as of 2020, an EQ-5D-Y index formula is not available for converting the health states into a single index value. The analysis for the PRO measures (EQ-5D-Y VAS and EQ-5D-Y index scores only if available) will be MMRM for the change in PRO score from baseline to each postdose visit for the HO population. The MMRM will include treatment, insulin usage, metformin usage, baseline HbA1c stratification, visit, visit-by-treatment interaction as fixed effects, and baseline score as a covariate. The variance-covariance structure for this model will be selected in the same order defined in Section 5.2. The EQ-5D-Y index score will be analyzed if it is available. Patient responses by EQ-5D-Y domains (mobility; looking after myself; doing usual activities; having pain or discomfort; feeling worried, sad, or unhappy) will also be descriptively examined. The above analyses will be calculated and reported for Age <13 years old, ≥ 13 years old, and ≤ 14 years old, >14 years old, and all age combined group. Please refer to the EQ-5D-Y User's Manual for appropriate descriptive reporting examples, VAS, and how to handle missing data.

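### As written, the exploratory biomarker model in SAP 5.16.6 cannot estimate the Week 13 and Week 26 treatment effects separately: it has a redundant visit-by-time term and no treatment-by-visit term

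*SAP*

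**What the plan says.** The objective is tied to two named visits. SAP 4.3 reads "Assess effect of dulaglutide on measures of insulin resistance, beta cell function, and serum adiponectin at Weeks 13 and 26", Protocol 6.3 has the same objective, and SAP 5.16.1 repeats both weeks in its list of exploratory parameters. Protocol 10.1.3 schedules the measures, ending with "estimated insulin sensitivity score at Weeks 0, 13, and 26", so there is one baseline and two post-baseline occasions.

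The model is in SAP 5.16.6. Besides stratification factors it lists "treatment, time, visit-by-time interaction as fixed effect, subject as a random effect, and corresponding baseline as a covariate". Treatment appears once, alone. The section names no within-patient covariance structure.

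The general rule in SAP 5.2 is different. Its default mixed model has "treatment (Dula 1.5, Dula 0.75, Placebo or Placebo/Dula 0.75), visit, and treatment-by-visit as fixed effects", and it applies unless something else is specified. The same section commits to a visit-specific display: "Treatment comparisons at the same visit will be displayed showing the LSmean and the 95% CIs for the treatment differences". The patient-reported outcome model in SAP 5.18 also carries the term that is absent here: "visit-by-treatment interaction as fixed effects, and baseline score as a covariate".

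**The concern.** In a repeated-measures model, treatment-by-visit is the term that lets the treatment difference vary between visits. Without it there is a single difference for all visits. SAP 5.16.6 has an interaction in that place, but it crosses visit with time, which in this design are the same thing.

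A programmer who follows the text therefore fits a term that does nothing and omits the term the objective needs. Two questions (is there an effect by Week 13, and what is it at Week 26) would receive one answer. HbA1c at the same visits is analysed with treatment-by-visit (SAP 5.11.1 and 5.16.2), so the biomarker results could not be set beside it week by week. SAP Section 3 lists the biomarker analyses among the changes made after FDA feedback, so their output will probably be read.

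**Working it through.** The plan states no figure here, so there is nothing to reproduce. The check is on the model terms.

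**Inputs.** From the documents: three arms (Protocol 9.3); post-baseline Weeks 13 and 26 (Protocol 10.1.3); three binary stratification factors, namely insulin use, metformin use and HbA1c stratum (SAP 5.2); the term list in SAP 5.16.6.

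**Step 1: algebra.** For arm a at visit v, the written model gives

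mean = constant + strata + τ(a) + π(v) + β × baseline,

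where π(v) absorbs time and visit-by-time. The difference from placebo is τ(a) − τ(placebo), with no v in it. With treatment-by-visit, a term γ(a,v) is added and the difference becomes τ(a) − τ(placebo) + γ(a,v) − γ(placebo,v), which can differ by week.

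**Step 2: design matrix.** The contrast examined is the Week 26 difference from placebo minus the Week 13 difference.

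| Model | Columns | Rank | Contrast |
|---|---|---|---|
| As written, time taken as the visit factor | 10 | 8 | zero vector |
| As written, time taken as continuous weeks | 9 | 8 | zero vector |
| Main effects only | 8 | 8 | zero vector |
| Treatment-by-visit in place of visit-by-time | 10 | 10 | non-zero |

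Visit-by-time leaves the rank at 8, so it adds nothing under either reading of time. The two weekly effects are constrained equal. With treatment-by-visit the matrix has full rank and the effects separate.

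**Step 3: what the common estimate is.** Let δ13 and δ26 be the true weekly differences and Δ = δ26 − δ13. The common estimate targets δ13 + wΔ, where w is the weight on Week 26. It is wrong by wΔ at Week 13 and by −(1 − w)Δ at Week 26. With complete data and equal variances, w = 0.5. The documents do not give Δ. Over an assumed range, Δ = 0 gives no error, Δ = 0.2 gives 0.10 in each week (opposite signs), and Δ = 0.4 gives 0.20.

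**Step 4: simulation.** Assumed, not from the documents: effects of 0.2 at Week 13 and 0.6 at Week 26 for both doses, subject and residual standard deviations of 0.7 each, Week 26 values missing at random, 150 replicates. The 50 per arm and the 10% and 20% rates match planning figures in SAP 5.1.

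| Missing at Week 26 | As written, both weeks | With treatment-by-visit: Week 13 | Week 26 |
|---|---|---|---|
| 0% | 0.392 | 0.188 | 0.595 |
| 10% | 0.370 | 0.186 | 0.584 |
| 20% | 0.362 | 0.186 | 0.606 |

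With no missing data, (0.188 + 0.595)/2 = 0.3915, which is the written model's 0.392 to rounding. With missing data the weight moves towards Week 13: w = (0.370 − 0.186)/(0.584 − 0.186) = 0.46 at 10%, and (0.362 − 0.186)/(0.606 − 0.186) = 0.42 at 20%.

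**Step 5: covariance.** Two visits have two variances and one covariance, so an unstructured matrix uses three parameters and fits them all. A random subject intercept on top adds a fourth parameter for the same three quantities and is redundant. Used alone, with independent residuals of equal variance, the intercept gives equal variances and one covariance: compound symmetry, the last fallback in SAP 5.2. SAP 5.16.6 does not say which is meant.

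**The case against.** The strongest reply is that this is a drafting slip. Visit-by-time has no sensible meaning, and the other spelled-out longitudinal models for continuous outcomes (SAP 5.1, 5.2, 5.15.7 and 5.18) include treatment-by-visit. A programmer who sees a redundant term beside the visit-specific display required by SAP 5.2 might well query it. That is probably how the wording arose. It does not settle the matter, because the SAP 5.2 default yields to any explicit specification and SAP 5.16.6 gives one. Where the sponsor wanted the default, as for weight and height in SAP 5.16.4, the text refers to it by section. The display commitment shows what is wanted but does not supply the term.

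SAP 5.14 also sends PK/PD analyses to a separate plan that is not available here. That plan might state the model correctly. It limits certainty about what will be run, but SAP 5.16.6 is still wrong as it stands.

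A reader might infer three stronger things that the documents do not support:

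- That no treatment effect can be estimated. It can: the model gives a common effect, valid for both weeks if the effect is constant.
- That Week 26 effects would be understated by some definite fraction. Any such figure comes from an assumed time course. The first biomarker visit is nine weeks after the Week 4 dose step (Protocol 7.1), and the effects at the two weeks could be similar.
- That the random subject effect is itself an identifiability error. It is redundant only if the unstructured covariance is also carried over from SAP 5.2. Alone, it can be fitted.

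**Conclusion.** The specification is wrong as written and should be corrected, whatever its origin. Followed literally, it constrains the dulaglutide-placebo difference to be equal at Weeks 13 and 26, contrary to the objective and to the planned visit-by-visit display. This follows from the term list alone and does not depend on the simulation.

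The size of any distortion cannot be derived from the documents. It is zero if the effect is constant, and about half the change between weeks if data are complete and variances equal. Otherwise the split depends on the fitted covariance and on missing values.

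The reach is small. These endpoints are exploratory and outside the hypotheses H1 to H12 in SAP 5.3. No alpha, sample size, primary result or key secondary result depends on them. A reader might take the point as a flaw in the HbA1c analysis; it is not, because that model uses treatment-by-visit or, for the treatment regimen estimand, a single-visit analysis of covariance.

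**What to change.** In SAP 5.16.6:

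- Replace visit-by-time with treatment-by-visit, and call the factor visit throughout.
- State that differences from placebo, for pooled dulaglutide and for each dose, are reported separately at Weeks 13 and 26.
- State one within-patient covariance: the SAP 5.2 sequence starting from unstructured, without a random subject effect.

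Referring to the SAP 5.2 model by section number, as SAP 5.16.4 does, would achieve most of this. If a separate PK/PD plan covers these endpoints, it should carry the same terms.

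The cost is a few sentences and no new data. There is some loss of precision. With two complete visits of equal variance and correlation ρ, the common difference has (1 + ρ)/2 times the variance of a single-week difference. At the simulated ρ = 0.49/(0.49 + 0.49) = 0.5 this is 0.75, so a weekly standard error is about 1/√0.75 = 1.15 times the common one. That is the price of answering the question asked. The change should be made before treatment assignments are opened, so that the model remains prespecified.
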